This study will include two groups of participants – persons with AUD and healthy controls. AUD subjects will have a current DSM 5 alcohol use disorder and will be actively drinking at least 50% above NIAAA recommended guidelines (women >10 drinks/week and men >20 drinks/week) and at least 5 binge drinking episodes in the past 30 days. Recent heavy drinking will be confirmed by PEth blood spot analysis ≥ 50 ng/mL. HC subjects will not meet DSM 5 criteria for AUD and will not be drinking above NIAAA recommended guidelines as confirmed by PEth blood spot analysis < 50 ng/mL. We expect to consent 450 subjects in order to accrue 150 subjects into the study procedures (N=75 for AUD and N=75 healthy controls). Historically, our retention in the CRU has been outstanding, with over 90% of subjects completing the protocol.

Additional Inclusion Criteria for all subjects:

- Nontreatment seeking volunteers;
- 21 – 60 years old;
- English speaking;
- 5th grade literacy to ensure ability to read study assessment instruments;
- no current serious psychiatric or health problems that would contraindicate study participation;
- BMI > 19 and < 40 ; medication dosing is not weight-adjusted. We have restricted the weight range of participants to reduce weight-associated variability;
- For women, negative urine pregnancy test prior to initiating MIFE treatment and agreement to use nonhormonal birth control for 2 weeks following last MIFE dose. A medical record of surgical sterilization or elevated FSH level confirming post-menopausal status is required to document non-childbearing potential;
- No adult seizure history;
- No serious alcohol withdrawal complications in prior alcohol withdrawal episodes;

- Some non-drinking days on 90-day TimeLine Followback Drinking Calendar;
- Study Physician and PI recommendation.

Exclusion criteria for all subjects:

- Women on hormonal birth control, or who are pregnant, nursing or planning pregnancy; women with unexplained vaginal bleeding;
- Current DSM 5 mood, anxiety or psychosis diagnosis or currently treated with psychiatric medication;
- Current substance use disorder except alcohol, marijuana (mild) or tobacco; current illicit drug use other than marijuana;
- History of serious alcohol withdrawal symptoms (e.g., seizures, hallucinations) or history of inpatient, medicated alcohol withdrawal management, and CIWA-Ar score at time of assessment ≥ 12 ;

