- c. Justification and safety information if non-FDA approved drugs without an IND will be administered.

During the alcohol sensitivity session, subjects will drink 3 doses of alcohol intended to bring their terminal BrAL to 0.10 mg/dL. Also, at the conclusion of the AMR session, participants can consume up to 5 standard drinks of their preferred alcohol type/brand, based on the number of alcohol reinforcers earned during the session. Beverages containing more than 7% alcohol are not regulated by the FDA; they are regulated by the Bureau of Alcohol, Tobacco, Firearms and Explosives. These beverages are legally sold to adults.

7. Study Statistics

- a. Primary outcome variables:

- adverse events and side-effects;

- fMRI changes in re-FC and CA across brain regions under GR regulatory control;
- Reduction in TSST-induced alcohol motivation and drinking;
- cardiovascular responses (HR, BP, ECG) during alcohol sensitivity sessions;
- alcohol euphoric and sedating effects during sensitivity sessions using VAS and Adjective Scales.

b. Secondary outcome variables will examine the effects of MIFE on a variety of psychological measures during alcohol abstinence, alcohol sensitivity sessions and outpatient visits. Secondary outcome measures include:

- Craving for alcohol during the inpatient stay, assessed using VAS, PACS, OCDS, and AUQ;
- Alcohol withdrawal symptom severity, assessed using the CIWA-Ar;
- Mood and personality assessments during the inpatient stay (BPRS, BDI, and BAI);
- Alcohol use during the outpatient follow-up, assessed using timeline followback self-report and PEth levels.

c. Statistical plan including sample size justification and interim data analysis.

Primary and secondary outcome variables will undergo data cleansing and Corrective/Preventive Measures based confirmation of accuracy and missing data. We will perform exploratory data analyses initially (stem-leaf displays, box plots, histograms, and Q-Q plots) and, if necessary, appropriate data transformations will be performed.

Power analyses: All power estimates are based on type I error =0.05, Power > 0.8. Specific aims are to compare GR antagonism versus placebo for:

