Aim 2. Reduction of alcohol withdrawal symptoms and craving, and improvement in low mood during early alcohol abstinence. Power for this aim was based on Vendruscolo et al (2015) (Fig 2A) in which MIFE effects were examined on VAS craving scores. Our hypotheses test if placebo (size = n) is different from MIFE. Comparing placebo effects (mean=11.5 (SD=2.1) to active drug effects (mean=9.3 (SD=2.2), total sample size required for the proposed aim is 39 (i.e.,20 in each group).

Aim 3. Reduction of stress-induced alcohol motivation and drinking. Power for this aim was based on Vendruscolo et al (2015) (Fig 2B) in which MIFE effects were examined on drinking during an outpatient treatment phase of the study. This calculation is based on between-subject calculation which overestimates the sample size requirement. Comparing placebo effects (mean (SEM) = 38.0 (10.2)) to active drug effects (mean (SD) = 27.5 (10.2)), total sample size required is 32. Using data from our AMR session in which mean number of drinks is 4.33 (sd = 3.17), we are powered to observe a 50% or greater reduction in drinks earned within the session.

Aim 4. Reduction of alcohol reward and sensitivity. Based on our preliminary data (4A1, Aim 3) and a sample of 50 GR antagonist vs 25 placebo subjects, we are powered to detect a difference of 3.0 degrees (3.3%) in peak skin temperature. Further, using data from our current alcohol sensitivity procedure (mean peak VAS total=168 (SD=118); mean peak liking=47.9 (SD=36.9)), we are powered to observe a 45 - 50% or greater reduction in alcohol subjective effects.

Aim 5. Side-effects. Power calculation is based on the assumption that the number of side-effect reports and adverse events follows a Poisson distribution. In preliminary data (Concept Investigator Brochure), an average of 12 events was reported in MIFE treated subjects. We estimate that 22 subjects in each group will give power > 0.8 for this statistical test.

Statistical Analyses: For aims 1 – 4, AUD and HC subjects will be separately grouped.

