Aim 3. AMR variables include: total number of alcohol drinks earned; total number of responses during the 60-minute session; distribution of responses for alcohol versus money; progressive ratio breakpoint for alcohol (maximum completed ratio value); response rate (responses/min) and response latency to compete the ratio for alcohol and money. We also measure alcohol craving using the Tiffany Craving Scale; these data will be summarized using peak score and area under the curve. The normality of the outcome measures will be examined first and two sample t-test, or equivalent non-parametric methods will be used to compare the outcomes between GR antagonist-treated group and placebo-treated group.

Aim 4: Subjective and physiological data will be collected repeatedly during the alcohol sensitivity session. We will test outcome measures between the two groups using mixed-effect linear regression with random intercept. Baseline measures will be examined as potential confounding factors and added to the model if needed. We will summarize the baseline adjusted area under the curve and peak values of the outcome measures and compare between the two groups using repeated measure ANCOVA model.

Aim 5: We use the SAFTEE to collect comprehensive side-effect information. We will construct negative binomial generalized linear regression model with the number of events as the dependent variable and grouping and other covariates as independent variables. The model will give the difference in the logs of expected numbers of side effect events between the two treatment groups. We will then also make comparisons taking into consideration the duration and severity of the side effects, which are both collected in SAFTEE for each reported side effect event. A summary side-effect score will be calculated as the sum of the duration multiplying the severity of each side effect event.

Secondary analyses: Another objective of this study is to generate power estimation for a full-size future clinical trial.

d. Early stopping rules.

Individual subjects will be discontinued from the protocol if they experience a moderate-to-severe adverse reaction to MIFE. They also will be discontinued for repeated rule violations on the CRU. The study will be discontinued if there is a pattern of MIFE-related AEs or SAEs.

8. Risks

a. Medical risks, listing all procedures, their major and minor risks and expected frequency.

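### Aim 3 calls its between-subject calculation conservative, but the planned AMR comparison is itself between-subject, and its power at 50:25 is just under the stated 0.8

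*Combined protocol and SAP*

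**What the plan says.** Section 7c opens its power analyses with "All power estimates are based on type I error =0.05, Power > 0.8". It does not say whether tests are one- or two-sided.

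The Aim 3 paragraph takes its sample size from a cited trial in which "MIFE effects were examined on drinking during an outpatient treatment phase of the study". It adds "This calculation is based on between-subject calculation which overestimates the sample size requirement", and then gives the inputs: "Comparing placebo effects (mean (SEM) = 38.0 (10.2" for placebo, against "active drug effects (mean (SD) = 27.5 (10.2)), total sample size required is 32". Next it turns to the study's own AMR data, mean 4.33 drinks with SD 3.17, and says "we are powered to observe a 50% or greater reduction in drinks earned within the session".

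Under Statistical Analyses, Aim 3, the AMR outcomes are to be compared as follows: "two sample t-test, or equivalent non-parametric methods will be used to compare the outcomes between GR antagonist-treated group and placebo-treated group". The Study Overview and Table 1 (section 4a) show one AMR session, on day 5, in AUD subjects only. The MIFE Administration text sets 2:1 allocation, and the Aim 4 power paragraph spells this out as 50 active and 25 placebo. On retention, section 5 reports past experience on the unit "with over 90% of subjects completing the protocol". The power section makes no allowance for dropout.

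**The concern.** Calling a between-subject calculation an overestimate makes sense only if the real analysis gains precision from repeated measures on the same person. If it does not, the sentence offers a margin that is absent. It also sits next to a figure of 32 that belongs to another outcome and another allocation ratio.

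Reduction in stress-induced alcohol motivation and drinking is a primary outcome in section 7a. The study also aims to supply power estimates for a later full-size trial. An unsupported statement about the design's efficiency could affect how a null AMR result is read and could carry over into that later calculation.

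**Working it through.** **1. Is any part of the Aim 3 comparison within-subject?** The documents describe none.
- AMR is run once per AUD subject, on day 5, after dosing began on day 1. No pre-drug AMR session is described.
- Craving is rated repeatedly within that session, but it is reduced to a peak and an area under the curve and then compared between arms.
- No baseline covariate is named for Aim 3, although Aims 1, 2 and 4 each allow for covariates.
- The within-subject comparison announced in the opening summary is for fMRI.

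**2. Reproduce the 32.** The inputs, from Power analyses, Aim 3, are means of 38.0 and 27.5 with 10.2 taken as a common SD. The difference is 38.0 − 27.5 = 10.5, so d = 10.5/10.2 = 1.03. Power comes from the noncentral t distribution, two-sided 0.05, with noncentrality = difference / [SD × √(1/n₁ + 1/n₂)].

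| Arms | Total | Noncentrality | Power |
|---|---|---|---|
| 16:16 | 32 | 10.5 / (10.2 × √(1/16 + 1/16)) = 2.91 | 80.4% |
| 22:11 | 33 | 10.5 / (10.2 × √(1/22 + 1/11)) = 2.79 | 77.0% |
| 24:12 | 36 | 10.5 / (10.2 × √(1/24 + 1/12)) = 2.91 | 80.7% |

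The 32 is therefore correct as a 1:1, two-sided figure with 10.2 as an SD. At exact 2:1 the first total to reach 80% is 36. A one-sided t-test at 1:1 would need only 26, so the stated 32 points to two-sided testing. If 10.2 were an SEM, the SD would be larger and both 32 and 36 would be too small. The documents do not give the group sizes needed to work out by how much.

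**3. Apply the same method to AMR drinks earned.** The inputs are mean 4.33, SD 3.17 assumed equal in both arms, and a 50% reduction. The difference is 0.5 × 4.33 = 2.165, so d = 2.165/3.17 = 0.683.

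| Arms (active:placebo) | Noncentrality | Power for a 50% reduction | Reduction detectable at 80% power |
|---|---|---|---|
| 50:25 | 2.165 / (3.17 × √(1/50 + 1/25)) = 2.79 | 78.6% | 2.205/4.33 = 50.9% |
| 45:23 | 2.165 / (3.17 × √(1/45 + 1/23)) = 2.66 | 74.7% | 2.310/4.33 = 53.4% |
| 45:22 | 2.165 / (3.17 × √(1/45 + 1/22)) = 2.63 | 73.4% | 2.345/4.33 = 54.2% |

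The last two rows bracket 90% completion, since 0.9 × 75 = 67.5. With the normal approximation, 50:25 gives 79.6% power and a detectable reduction of 50.2%. At exact 2:1 the first total to reach 80% by the t-test is 52:26, or 78, with power 80.2%.

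**The case against.** The strongest reply is that the AMR claim is right at the precision it is stated. At 50:25 the detectable reduction is 50 to 51%, and the gap to 80% power is about one percentage point. That stands for complete data.

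The gap also depends on assumptions the plan does not state.
- **Sidedness.** Hypothesis 3a is directional. One-sided, power would be 86.8% at 50:25 and 83.0% at 45:22. Two-sided remains the more consistent reading, because the 32 reproduces that way.
- **Equal SDs.** Drinks earned is capped at ten half-drink reinforcers, so halving the mean may change the spread. An SD of 3.17 around 4.33 is impossible on a 0 to 5 scale, where the maximum is √(4.33 × 0.67) = 1.70. Under this procedure it would have to count reinforcers from 0 to 10. As an illustration, an active-arm SD of 2.9 gives 80.1% by Welch's test at 50:25, and 2.5 gives 82.9%.
- **Dropout.** The plan reports completion above 90% for the whole protocol, and AMR falls on day 5 of 7, so 67 to 68 subjects with AMR data is towards the pessimistic end.

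A reader might infer that Aim 3 needs 78 subjects rather than 32, or that the 32 is a miscalculation. The documents do not support either reading. The 32 is offered for outpatient drinking, never for AMR drinks earned, and it follows from its own inputs. Nor does the plan set 32 against the 75 AUD subjects and claim a large margin. The following sentence discloses that only a reduction of 50% or more is detectable in AMR.

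None of this supports the statement that the calculation is an overestimate.

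**Conclusion.** The point holds as a correction to the power statement. The sentence claiming an overestimate has no basis in the design, because the AMR comparison is between-subject throughout. The 32 is internally correct, but it applies to a different outcome, to 1:1 allocation, and only if 10.2 is an SD. About 36 would be needed at the planned 2:1 on the same condition.

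For AMR drinks earned, power for a 50% reduction is 78.6% with all 75 AUD subjects and about 73 to 75% if 90% complete, against a stated target above 0.8. These figures assume a two-sided 0.05 t-test and equal SDs of 3.17. The complete-data shortfall is narrow and could vanish under a one-sided test or a somewhat smaller active-arm SD. On the stated assumptions, the shortfall after 10% loss is clear. It is not evidence that the trial is too small for its purpose.

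**What to change.** In section 7c, Power analyses, Aim 3:
- Delete the sentence saying the calculation overestimates the requirement.
- Drop the 32. Alternatively, check the source, settle whether 10.2 is an SEM or an SD, and then label the figure as a 1:1 requirement for outpatient drinking.
- State for AMR drinks earned that 50:25 detects about a 51% reduction with 80% power by a two-sided 0.05 t-test, or about 53 to 54% if 90% complete. Give the equal-SD assumption and say whether 4.33 and 3.17 count standard drinks or half-drink reinforcers.

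Enrolment, allocation and analysis stay as they are. The cost is a slightly less favourable stated figure.

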Aim 1. Changes in rs-FC and CA across key brain regions under GR gene regulatory control. From the data obtained in preliminary fMRI studies (4.1c), we extracted each subject's connectivity measure (r value converted to Fisher Z score) between left NAcc and 6 mm ROI in the right inferior parietal cortex. Mean and SD connectivity measurement of 0.134, .082 were obtained from alcohol subjects and -.058, .062 were obtained for controls. We made the following assumptions: (a) t1 connectivity will be that of Alc mean (.134) for drug and placebo groups; (b) t2 connectivity will not change for placebo group; (c) t2 connectivity for the drug group will normalize by at least one-third toward HC values, ie: $t2(\text{expt group}) = \text{Alc mean} - (\text{Alc mean} - \text{HC mean})/3 = 0.07$; (d) SD for each cell is the pooled SD (.076); (e) the correlation between repeated measurements (t1 and t2) is 0.5. Using these assumptions a partial eta squared of 0.1563 was calculated for the group x time interaction for a repeated measure ANOVA. Using this estimate with GPower3 (Faul et al., 2007) software we calculated that 25 subjects per group will result in 83% power for detecting a significant interaction at $p < .05$.

Cue-induced Activation: Myrick et al (2008) showed that AUD compared with HC subjects showed increased ventral striatal activation to alcoholic beverage pictures relative to neutral beverage pictures, and that treatment with a combination of naltrexone and ondansetron significantly decreased CA activation. Their paper provided mean and SD information for placebo and drug group ventral striatal activation that was used to estimate effect size for the present proposal for the interaction for a repeated measures anova with between group factor of drug treatment (placebo vs drug) and within group measure of time (baseline and after

treatment). Because this study was performed on a 1.5T scanner, the contrast to noise ratio was multiplied by a factor of 1.3, as described by Hoenig et al.,(2005) to accurately reflect scanning at 3T in the present study. These calculations revealed a partial eta squared value of 0.185, assuming that the drugs in the present study produce at least a comparable effect to the naltrexone/ondansetron treatment. Using this estimate with GPower3 (Faul et al., 2007) software we calculated that 25 subjects per group will result in 90% power for detecting a significant interaction at $p < .05$.

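### Aim 4's 45–50% detectable reduction is not supported by its printed inputs: at 50 vs 25, unadjusted and two-sided, 80% power needs about 49% for peak VAS total and 54% for peak liking

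*Combined protocol and SAP*

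**What the plan says.** Section 7c, Power analyses, opens with a rule for every aim: "All power estimates are based on type I error =0.05, Power > 0.8". It does not say whether tests are one- or two-sided.

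The Aim 4 paragraph uses "a sample of 50 GR antagonist vs 25 placebo subjects". It gives peak VAS total as mean 168 (SD 118) and peak liking as mean 47.9 (SD 36.9), and concludes that "we are powered to observe a 45 - 50% or greater reduction in alcohol subjective effects". It does not say which end of the range belongs to which measure. It gives no SD for the drug arm and no correlation between baseline and peak.

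Section 7c, Statistical Analyses, Aim 4, plans a mixed-effects model, and an ANCOVA on summary measures: "We will summarize the baseline adjusted area under the curve and peak values of the outcome measures". On covariates it says "Baseline measures will be examined as potential confounding factors and added to the model if needed".

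Section 7a lists the euphoric and sedating effects of alcohol among the primary outcomes.

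**The concern.** The Aim 4 statement looks like a result computed from the two means and SDs beside it, yet the obvious calculation from those figures does not give it. The SDs are large relative to the means (118/168 = 0.70 and 36.9/47.9 = 0.77), and a 2:1 split of 75 subjects is less efficient than an equal split. Both make a 45% reduction hard to reach with 80% power.

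At stake is how far a reader can rely on the stated sensitivity for a listed primary outcome. Section 7c also says the study should yield power estimates for a later full-size trial, so a detectable effect whose basis cannot be traced may be carried forward.

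**Working it through.** **Inputs.** All are from Section 7c: alpha 0.05; power above 0.8; 50 vs 25; peak VAS total 168 (SD 118); peak liking 47.9 (SD 36.9). My assumptions, because the plan is silent, are a two-sided test, the same SD in both arms and no baseline adjustment.

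**Formulas.** For a proportional reduction p, the standardised effect is d = p × mean / SD. The noncentrality is d / √(1/50 + 1/25) = d / 0.2449. With 73 degrees of freedom the two-sided critical value is 1.993. Power is the probability that a noncentral t exceeds it.

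**Trying to reproduce 45–50%.**

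| Measure | Reduction | Difference | d | Noncentrality | Power |
|---|---|---|---|---|---|
| VAS total | 45% | 75.6 | 0.641 | 2.616 | 73.3% |
| VAS total | 50% | 84.0 | 0.712 | 2.906 | 81.8% |
| Liking | 45% | 21.6 | 0.584 | 2.385 | 65.3% |
| Liking | 50% | 23.95 | 0.649 | 2.650 | 74.4% |

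Three of the four combinations miss 0.8. The one that passes is VAS total at 50%.

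**Reduction detectable with 80% power.** This needs d = 0.695.
- VAS total: 0.695 × 118 = 82.1 points; 82.1 / 168 = 48.8%.
- Liking: 0.695 × 36.9 = 25.7 points; 25.7 / 47.9 = 53.6%.

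**What the unstated assumptions could do (50 vs 25).**
- One-sided 0.05: required d is 0.615, so the detectable reductions are 43.2% and 47.4%.
- Baseline adjustment: the SD is multiplied by √(1 − ρ²), with 72 degrees of freedom. VAS total at 45% reaches 80% when ρ is about 0.39: 118 × 0.921 = 108.7, and 75.6 / 108.7 = 0.696. Liking at 50% needs ρ of about 0.36: 36.9 × 0.933 = 34.4, and 23.95 / 34.4 = 0.696. Liking at 45% needs about 0.54.
- Over assumed correlations, the detectable reductions are 46.6% and 51.1% at ρ = 0.3, and 42.3% and 46.4% at ρ = 0.5.
- Drug-arm SD shrinking in proportion to its mean (Welch test, simulated): 82.6% power for VAS total at 45%, 84.2% for liking at 50% and 75.0% for liking at 45%.
- An equal split of the same 75, two-sided: detectable reductions of 46.1% and 50.5%. This is close to the printed range but contradicts the stated 50 vs 25. Whether it is where the range came from cannot be known.

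**Aim 3 label.** The Aim 3 paragraph attaches SEM to 10.2 for placebo (mean 38.0) and SD to 10.2 for active drug (mean 27.5). Taking it as an SD in both arms, d = (38.0 − 27.5) / 10.2 = 1.029. Two-sided, 16 + 16 gives 80.4% and 15 + 16 gives 79.1%, so the printed total of 32 reproduces.

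**The case against.** The strongest reply is that the shortfall comes from assumptions the plan never made. Hypothesis 4a is directional. The planned analysis uses baseline-adjusted summaries. A drug that lowers the mean may also lower the SD. If 45% is read as VAS total and 50% as liking, any one of these could restore 80% power. This stands, and it rules out saying that the sponsor made an arithmetic error. It does not rescue the statement as printed. None of these assumptions is given for Aim 4, whereas Aim 1 does print its repeat-measure correlation of 0.5. Baseline terms also enter the Aim 4 model only where judged necessary.

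A second reply is that the range is rounded and unassigned, and 48.8% for VAS total lies inside it. That is correct. Only liking falls outside, by 3.6 points. It would be wrong to say that both measures miss throughout, or that each detectable reduction is some 4 points above its own stated figure. The latter needs a pairing that the text does not make.

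A reader might also infer that the other aims prove a two-sided convention. The support is thin. Aim 1's result, "we calculated that 25 subjects per group will result in 83% power for detecting a significant interaction", comes from an interaction F test, which has no direction. Aim 2's wording, "Our hypotheses test if placebo (size = n) is different from MIFE", concerns Aim 2 alone. Aim 3's 32 reproduces two-sided only if its questioned label is an SD. Two-sided is used here as the ordinary default.

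**Conclusion.** The point holds as a minor one. From the printed inputs, on a two-sided, common-SD, unadjusted basis, 50 vs 25 does not give power above 0.8 across a 45–50% reduction. VAS total gets there at about 49%. Liking gets there at about 54% and falls short over the whole range, with 65.3% to 74.4% power. The result depends on those three assumptions, and the planned baseline-adjusted analysis may do better by an amount that the documents do not allow one to compute.

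Two stronger readings are not supported. One is that the trial is underpowered for subjective effects and needs more subjects: the gap is a few percentage points of detectable reduction and closes under plausible but unstated assumptions. The other is that Aim 3's 32 is wrong: it reproduces with an SD in both arms, so the mixed labels look like a slip. Which label matches the cited source cannot be settled from the documents.

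**What to change.** In Section 7c, Power analyses, Aim 4, do one of the following.

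- Replace the 45–50% statement with: *With 50 vs 25, two-sided alpha 0.05, a common SD and before baseline adjustment, there is 80% power to detect reductions of about 49% in peak VAS total and 54% in peak liking; the planned baseline-adjusted analysis may detect smaller reductions.*
- Keep 45–50% and print the assumption that delivers it, measure by measure. Examples are a one-sided test, or a baseline correlation of about 0.39 for VAS total at 45% and 0.36 for liking at 50%.

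Separately, check Aim 3's 10.2 against its source. If it is an SD, label both arms SD and keep 32. If it is an SEM, convert it using the source's arm sizes and recompute or remove 32.

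The cost is a wording change and one source check. The Aim 4 figures become slightly less favourable or gain a stated condition.
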